6.1.7.2 On-Target Toxicities

The brain appears to be the only organ to express tau at significant levels. Tau is an intracellular protein mainly expressed in neurons, although lower levels can be found in astrocytes and oligodendrocytes. ABBV-8E12 is directed against extracellular tau and no function of extracellular tau has been reported. No cellular uptake of the mouse version of ABBV-8E12 antibody bound to tau aggregates was detected in preclinical studies.³² The likelihood of adverse on-target side effects of an anti tau immunotherapy is therefore anticipated to be low.

6.1.7.3 Non-Specific Off-Target Toxicities

Potential toxicities resulting from the non-human origin of ABBV-8E12 include allergic reactions or infusion reactions, including anaphylaxis or anaphylactoid reactions, flu-like symptoms, including fever, fatigue or loss of appetite, or rash. ABBV-8E12 is lacking the Fragment Crystallizable (Fc) effector function activity and therefore Fc-mediated antibody-dependent cellular cytotoxicity and complement-dependent cytotoxicity is not expected. In addition, ABBV-8E12 exhibited a favorable in vitro immune-safety profile. No infusion reactions have occurred in the single dose PSP clinical study or in the Expanded Access protocol (Studies C₂N-8E12-EA-001 and C₂N-8E12-DE-003).

6.1.7.4 Allergic Reactions Management

Subjects will be closely monitored for treatment-related adverse events, including allergic reactions, during the infusion. Subjects should be monitored on site for at least 30 minutes after the end of study drug infusions. Longer observation periods and more frequent vital sign checks may be required in subjects who experience infusion reactions.

Severe or life-threatening allergic reactions require the immediate interruption of ABBV-8E12 treatment and permanent discontinuation from further treatment. Appropriate medical therapy including epinephrine, corticosteroids, IV antihistamines,

bronchodilators, and oxygen should be available for use in the treatment of such reactions. Subjects should be carefully observed until the complete resolution of all signs and symptoms.

Moderate infusion reactions resolving with supportive care should be discussed with the TA MD, and a reduction of the infusion rate for future administrations can be considered.

6.1.7.5 Management of Adverse Events of the Nervous System

Subjects will be closely monitored for adverse events suggesting neurotoxicity. A drug related adverse event is an event that is judged by the investigator or AbbVie to have a "reasonable possibility" of being related to the study drug.

Severe or life-threatening drug related adverse events of the nervous system will require discontinuation from further treatment with ABBV-8E12 and prompt notification of the AbbVie TA MD. Appropriate medical therapy will be initiated and subjects will be followed up until the resolution.

Clinically significant treatment-emergent neurological abnormalities or MRI findings will prompt notification of the AbbVie TA MD; subjects will be considered for discontinuation if clinically indicated, and may be permitted to continue in the study only after a management plan is discussed with the AbbVie TA MD.

6.1.8 Collection of Data Regarding Known Complications of the Disease Under Study

Natural progression of PSP (including new or worsening neurological symptoms and signs) is expected in the subjects. Disease progression will be assessed at pre-determined intervals throughout the treatment period by standardized criteria (such as the PSPRS, SEADL, UPDRS Part II, CGI-S, NNIPPS-PPS) and recorded on the corresponding CRF pages for purposes or risk/benefit determinations. Therefore, "disease progression" or other similar verbatim terms related to disease status SHOULD NOT be recorded on the adverse event CRF pages. Similarly, since falls are a core component and defining feature of PSP (Steele-Richardson-Olszewski Syndrome), falls will not be recorded as

adverse events unless they lead to other injury or represent a change in frequency or character before enrollment in this study.

Similarly, the slow progression of pre-existing (before enrollment in this study) disease-related signs and symptoms clearly associated with the disease during the treatment period will not be reported as adverse events unless these signs and symptoms are judged by the Investigator to have become unusually severe or accelerated, or if the Investigator suspects the deterioration of disease-related signs and symptoms to be potentially related to the investigational drug. If there is any uncertainty about the worsening of an adverse event being due solely to the disease under the treatment protocol, it should be reported as an adverse event or SAE as appropriate.

Discontinuation from this treatment protocol because of progression or deterioration of the disease should be recorded on the protocol Termination CRF page as discontinuation due to "disease progression" and NOT as discontinuation due to an adverse event.

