4.4 Interim Analyses

Safety Interim Reviews

Regular interim safety reviews will be performed for this study by the DMC. An independent statistical and data analysis center (SDAC) will be responsible for generating and providing unblinded statistical tables, figures, and listings to the DMC for the interim safety reviews. To maintain the integrity of the trial, a specific data access plan with a strict firewall will be in place to protect the unblinded data and the details will be described in the DMC charter.

Before database lock of Study M15-562, safety reviews of Study M15-563 will follow the same schedules as Study M15-562. DMC safety reviews after subjects from Study M15-562 roll over to Study M15-563. After the last scheduled DMC safety review meeting for Study M15-562, independent DMC safety review meetings for Study M15-563 will occur every 6 months. The database snapshots will be taken for the safety interim reviews.

The DMC will communicate their recommendations to the AbbVie Contact regarding continuing, modifying or terminating the trial due to safety concerns in accordance with the DMC charter.

The following analyses will be conducted for the safety interim reviews:

- Subject disposition and baseline demographics (gender, race, ethnicity, age, weight, height, body mass index)
- Treatment emergent adverse events analysis: overview, by system organ class (SOC) and preferred term (PT), SAE by SOC and PT, AEs leading to discontinuation, AEs with reasonable possibility
- Laboratory mean change analysis and summary of potentially clinically significant (PCS) events
- Mean change analysis of vital signs and summary of PCS events of vital sign values
- Mean change analysis of electrocardiogram (ECG) and summary of PCS events of ECG values
- Summary of concomitant medications
- Summary of PK parameters (as available)
- Exposure-response analyses on any safety endpoint if necessary
- Summary of Columbia Suicide Severity Rating Scale (C-SSRS)
- Summary of MRI results

More details of safety interim analyses will be specified in the DMC Charter.

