10.2.1 Adverse Event Overview

The number and percentage of subjects experiencing one or more adverse events in the following adverse event categories will be summarized for each treatment group and overall subjects in both Stand-Alone data set and the Cumulative data set. No comparisons of treatment groups will be performed.

- Any TEAE
- Any TEAE that was rated reasonable possibility of being related to study drug by the investigator
- Any severe TEAE
- Any serious TEAE
- Any TEAE that led to discontinuation of study drug
- Any fatal TEAE
- All deaths

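### Protocol 6.1.8 bars discontinuations for disease deterioration from being recorded as due to an adverse event, with no exception for deterioration that the same section makes an adverse event

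*Protocol*

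**What the plan says.** **Protocol 6.1.8, second paragraph.** Slow worsening of pre-existing PSP signs is normally not reported as an AE. One exception is worsening "judged by the Investigator to have become unusually severe or accelerated". A second limb makes it an AE "if the Investigator suspects the deterioration of disease-related signs and symptoms to be potentially related to the investigational drug". Where it is uncertain whether a worsening is due to the disease alone, it is to be reported as an AE or serious AE.

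**Protocol 6.1.8, last paragraph.** A stop for progression or worsening of the disease is entered as follows: "recorded on the protocol Termination CRF page as discontinuation due to 'disease progression' and NOT as discontinuation due to an adverse event". No exception follows, and none appears elsewhere in either document.

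**Protocol 6.1.7.5.** "Severe or life-threatening drug related adverse events of the nervous system will require discontinuation from further treatment with ABBV-8E12".

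**What is collected.** Protocol 6.1 has the investigator record, for each AE, its relationship to study drug and any action taken. Protocol 5.4.1 collects a primary reason for discontinuation and any other reasons.

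**What is reported.** SAP 7.0 summarises premature discontinuation of study drug or study by primary or any reason. SAP 10.2.1 has a row for "Any TEAE that led to discontinuation of study drug". SAP 10.2.2 repeats that category by system organ class and preferred term, and SAP 10.2.3 adds a listing. Protocol 8.1.2.2 plans the same kind of table. For the DMC, SAP 4.4 lists "AEs leading to discontinuation" as one item among several.

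**The concern.** Within one section, the same clinical event can be an AE, even a drug-suspected one, and yet be barred from being recorded as the AE that ended participation. Long-term safety and tolerability is a primary objective. Protocol 6.1.8 itself expects new or worsening neurological signs from natural progression, so harm to the nervous system and the disease can look alike. Worsening that the investigator thinks may be due to the drug, and that is bad enough to end participation, is the subset a safety reader most needs to find under the right heading. If sites obey the last paragraph, its recorded reason becomes disease progression. If some sites obey it and others use judgement, the recorded reasons are not comparable across sites.

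**Working it through.** No arithmetic applies. The rule concerns recording, and the documents give no rate of such discontinuations. The check follows one subject whose PSP signs worsen in a way that 6.1.8 makes an AE and who then stops.

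| Step | Governing text | Result if 6.1.8 is followed literally |
|---|---|---|
| AE page | Protocol 6.1.8, second paragraph; 6.1 | Event entered, with relationship and action taken |
| Termination page | Protocol 6.1.8, last paragraph | Reason entered as disease progression; AE attribution ruled out |
| TEAE tables | SAP 10.2.1, 10.2.2 | Event counted |
| Drug-related TEAE tables | SAP 10.2.1, 10.2.2 | Counted if rated a reasonable possibility |
| Serious TEAE tables | SAP 10.2.1, 10.2.2 | Counted if serious |
| Disposition by reason | SAP 7.0 | Appears under disease progression, not AE |
| TEAE that ended study drug: row, table, listing | SAP 10.2.1 to 10.2.3; Protocol 8.1.2.2 | Depends on the source of the flag, which is not stated |
| DMC item on AEs leading to discontinuation | SAP 4.4 | Same dependence |

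The two possible sources of the flag give different results:

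1. **Termination-page reason.** The event is missing from the discontinuation row, the table, the listing and the matching DMC item.
2. **AE-page action taken.** The event is counted there, but the disposition summary gives disease progression for the same subject, so two planned outputs disagree. The event could still be lost if sites carried the 6.1.8 instruction over to the action-taken field.

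Protocol 6.1.7.5 meets the same rule. If a severe drug-related nervous-system event consists of worsening PSP signs, 6.1.7.5 makes the AE the ground for stopping treatment. When the subject leaves the study, the last paragraph of 6.1.8 tells the site not to record it as such. The passages need to be reconciled on recording; whether treatment should stop is not at issue.

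The entry for other reasons in Protocol 5.4.1, with the any-reason tabulation in SAP 7.0, would help only if AE could be entered as a further reason. The prohibition in 6.1.8 points against that.

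**The case against.** The best defence has three parts.

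**The paragraph can be read narrowly.** Deterioration of the disease can mean the underlying course of PSP, so a stop attributed to the drug would not be because of the disease and the rules would not collide. This has some force for drug-suspected worsening, although the text never says so and the preceding paragraph uses the same word for that worsening. It does not rescue the other limb: an unusually severe or accelerated worsening is an AE under 6.1.8 whatever its cause, and it is still deterioration of the disease.

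**The instruction governs one field.** The SAP tables count TEAEs that ended study drug, which is an AE-level item, and action taken is recorded for each AE. Deriving the flag from the AE page may already be what is intended. This stands: loss from those tables is a risk that depends on an unstated source, and a reader who inferred a demonstrated bias in the safety results would go beyond the documents.

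**The signal stays visible.** A reader might infer that these events vanish from the DMC package. They do not. SAP 4.4 lists the TEAE overview, TEAEs by class and term, serious AEs and AEs with a reasonable possibility separately from AEs leading to discontinuation, and Protocol 5.5.5 gives the DMC full data access as needed. At most, the item on AEs leading to discontinuation loses the event; any reason shown in the disposition item would read disease progression.

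**Conclusion.** The point holds as a conflict in the recording rules with one direct consequence and one conditional consequence. The direct consequence is that, followed literally, the last paragraph of 6.1.8 misclassifies these discontinuations in the SAP 7.0 summary by reason. The conditional one is that they are missing from the AE-discontinuation outputs and the matching DMC item if the flag comes from the Termination page. The TEAE outputs keep the event, as do the drug-related outputs when it is rated a reasonable possibility and the serious AE outputs when it is serious.

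The size cannot be stated. The documents give no rate for such discontinuations, and the enrolment ceiling of 378 says nothing about how many subjects would stop for this reason. It would also be wrong to express the effect as lost power: SAP 10.1 and 10.2.1 plan no between-group comparisons for these outputs, so the stake is correct counts and visibility of a signal.

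The conclusion assumes that sites apply the last paragraph as written. It should be corrected, because a stated rule contradicts its own section and the remedy is small.

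**What to change.** 1. **Protocol 6.1.8, last paragraph, and the CRF completion guideline.** Limit the instruction to deterioration not reported as an AE under the preceding paragraph. Where it was so reported, record the discontinuation as due to that AE, with disease progression as an additional reason where appropriate. This also reconciles the recording with 6.1.7.5.
2. **SAP 10.2.** State that the flag for a TEAE that led to discontinuation of study drug is derived from the action taken on the AE page, whatever reason stands on the Termination page.

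The cost is one sentence in the protocol and guideline and one derivation line in the SAP. The change affects recording and derivation only and alters no stopping rule. The count of AE discontinuations may come out slightly higher.

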6.2 Product Complaint

6.2.1 Definition

A Product Complaint is any Complaint (refer to Section 6.0 for the definition) related to the biologic or drug component of the product.

For a product this may include, but is not limited to, damaged/broken product or packaging, product appearance whose color/markings do not match the labeling, labeling discrepancies/inadequacies in the labeling/instructions (example: printing illegible), missing components/product or packaging issues.

Any information available to help in the determination of causality to the events outlined directly above should be captured.

6.2.2 Reporting

Product Complaints concerning the investigational product must be reported to the Sponsor within 1 business day of the study site's knowledge of the event via the Product Complaint form. Product Complaints occurring during the study will be followed-up to a satisfactory conclusion. All follow-up information is to be reported to the Sponsor (or an authorized representative) and documented in source as required by the Sponsor. Product Complaints associated with adverse events will be reported in the study summary. All other complaints will be monitored on an ongoing basis.

Product Complaints may require return of the product with the alleged complaint condition. In instances where a return is requested, every effort should be made by the investigator to return the product within 30 days. If returns cannot be accommodated within 30 days, the site will need to provide justification and an estimated date of return.

The description of the complaint is important for AbbVie in order to enable AbbVie to investigate and determine if any corrective actions are required.

8.0 Statistical Methods and Determination of Sample Size

The data analysis will be grouped by assigned treatment sequences/group in Studies M15-562/M15-563: 2000/2000 mg, 4000/4000 mg, placebo/2000 mg, and placebo/4000 mg. If the treatment effect between each ABBV-8E12 dose and placebo is statistically significant at Week 52 in Study M15-562, the 2000/2000 mg and 4000/4000 mg groups could be combined as the early-start ABBV-8E12 treatment group, and the placebo/2000 mg and placebo/4000 mg groups could be combined as the delayed-start group for the delayed-start analysis. Details of the analyses will be specified in the statistical analysis plan (SAP).

Data Sets for Efficacy Analyses

Two data sets will be used for the efficacy analysis: an intent-to-treat (ITT) data set and a delayed-start data set.

ITT Data Set: The Study M15-563 ITT data set consists of all subjects who received any dose of study drug in Study M15-563. This is the primary efficacy analysis set for this

study. All efficacy analyses for Study M15-563 alone will be conducted on the ITT set unless otherwise specified.

Delayed-Start Data Set: The delayed start analysis data set includes efficacy data from both Studies M15-562 and M15-563. All subjects from Study M15-562 ITT data set will be included, regardless if they enroll in Study M15-563 or not. Subjects who complete Study M15-562 and rollover to Study M15-563 but have a gap of more than 8 weeks between study drug infusions before enrolling into Study M15-563 will be excluded from this analysis set.

Data Sets for Safety Analyses

The safety data sets will consist of all subjects who received any dose of study drug in Study M15-563. For the safety analyses, the actual treatment received will be used instead of the treatment assignment at the time of randomization. There are 2 safety datasets: a Stand-Alone safety data set and a cumulative safety data set as described below.

Stand-Alone Data Set: The stand-alone data set is the primary data set for the safety analysis, and will contain data from Study M15-563 only, regardless of the treatment received in Study M15-562. Baseline will be the last observation on or before the first dose of ABBV-8E12 in Study M15-563. If no Baseline is recorded in Study M15-563, the last value in Study M15-562 will be used as the Baseline.

Cumulative Data Set: The cumulative data set will consist of data from both Study M15-562 and Study M15-563. It is the secondary data set for safety analyses. For subjects who were in the placebo group in Study M15-562, their safety data from Study M15-562 will not be included in the cumulative data sets but their safety data from Study M15-563 will be included. For Study M15-562 placebo subjects, Baseline will be the last observation prior to the first dose of study drug in Study M15-563. For subjects who were in ABBV-8E12 treatment groups in Study M15-562, Baseline for the safety analyses will be their Baseline in Study M15-562.

8.1 Statistical and Analytical Plans

8.1.1 Efficacy Analyses

All efficacy analyses of comparisons will be performed with a 2-sided test at the significance level of 0.05 unless otherwise specified. All efficacy assessments that are taken no more than 45 days after the last dose of study drug will be included in the efficacy analysis.

The primary efficacy variable is the PSPRS total score in the Study M15-563 ITT analysis. The primary analysis model is a likelihood-based, mixed-effect model, repeated measures (MMRM) analysis of the PSPRS total score at Study M15-563 Baseline and each post-baseline observation using all observed data. The model will consist of fixed, categorical effects for treatment, site, visit, and treatment-by-visit interaction. An unstructured (co)variance structure will be used to model within-subject errors. Satterthwaite's approximation will be used to estimate denominator degrees of freedom, and the Type III sum-of-squares for the Least Square (LS) means will be used to estimate treatment group differences. The differences for placebo/2000 mg vs 2000/2000 mg and for placebo/4000 mg vs 4000/4000 mg at Study M15-563 Baseline and at the end of the Study M15-563 Treatment Period will be presented with a 95% confidence interval. Contrasts of treatment effects for other visits will be conducted as well. This MMRM analysis will be applied to each efficacy variable with repeated measurements. Details of the analysis will be described in the SAP.

The delayed-start analysis will be conducted on the change from Baseline in Study M15-562 up to Week 52 in Study M15-563 on the PSPRS total score. An MMRM analysis model will be used. The model will consist of fixed, categorical effects for treatment, site, visit, and treatment-by-visit interaction, with continuous fixed covariates for baseline PSPRS total score and the baseline score-by-visit interaction. An unstructured (co)variance structure will be used to model within-subject errors. Satterthwaite's approximation will be used to estimate denominator degrees of freedom, and the Type III sum-of-squares for the LS means will be used to estimate treatment

group differences. The primary comparisons will be the contrasts between an ABBV-8E12 dose group and the placebo group at Week 52 in both Study M15-562 and Study M15-563, and non-inferiority analysis of treatment effects at Week 52 between the 2 studies. If only one of the ABBV-8E12 dose groups in Study M15-562 is statistically significantly different from placebo at Week 52, the delayed-start analysis will be conducted only for that dose. If treatment effects at Week 52 in Study M15-562 are statistically significant for both ABBV-8E12 doses (based on the primary analysis defined in the Study M15-562 SAP), the combined early-start groups and the combined delayed-start groups will be used for the delayed-start analysis. If neither ABBV-8E12 dose is statistically significantly different from the placebo at Week 52 in Study M15-562, the delayed-start analysis will not be conducted. No multiplicity adjustment will be made for the delayed-start analysis based on combined groups or a selected ABBV-8E12 dose. Details of the analysis will be specified in the SAP.

The analysis on secondary and exploratory efficacy variables will be detailed in the SAP.

8.1.2 Safety Analyses

Comparisons between treatment groups (Studies M15-562/M15-563) of interest will be performed with a 2-sided test at the significance level of 0.05 unless otherwise specified.

Unless otherwise specified, treatment group differences in continuous safety variables (e.g., change from Baseline to final observation on laboratory tests) will be assessed using an analysis of variance (ANOVA) model with treatment group as the main effect, and the treatment group differences in binary safety variables will be evaluated using Fisher's exact test.

A treatment-emergent adverse event (TEAE) is defined as any adverse event that begins or worsens in severity on or after the date of the first dose of study drug and no more than 20 weeks after the date of the last dose of study drug.

All other safety assessments that are taken no more than 45 days after the last dose of study drug will be included in the safety evaluation of the Treatment Period, and all safety

assessments that are taken more than 45 days but not more than 20 weeks after the last dose of study drug will be included in the safety evaluation for the Post-treatment Follow-up Visit.

